5.3 ENROLLMENT AND RANDOMIZATION

There will be 18 participants per group (15 vaccine recipients and 3 placebo recipients). Investigators will be blinded to vaccine versus placebo within each group but not across groups. Participants will be block randomized. Group 1 (with a prime of Env-C Plasmid DNA IM alone at weeks 0, 4, 12) will be fully enrolled first. After the 18 participants in Group 1 are enrolled, the remaining groups, 2-7, will begin enrolling participants. Once 24 participants in Groups 2-7 have been enrolled (four from each group) and received their first vaccinations, enrollment and vaccinations in Groups 2-7 will be paused for the time it takes the PSRT to review (typically 3 to 14 days) blinded safety data from these 24 participants covering the period immediately after their first vaccination through Day 7. If it is determined to be necessary by the PSRT, the MHRP SMC will be consulted to review unblinded data to provide a recommendation on continuing enrollment.

When safety has been confirmed with PSRT review, the remaining 14 participants in each of Groups 2-7 will be enrolled, and vaccinations will continue until the first 24 participants in Groups 2-7 (four per group) have received their first boost dose (at 20 weeks—to create a time gap between boost vaccinations of the first cohort and the remaining study participants).

A second scheduled pause (this pauses boost vaccinations only; prime vaccinations can continue) will occur for Groups 2-7 after the same set of participants reviewed during the first scheduled pause (the first 24 participants (four per group) from Groups 2-7) has received its first boost (Group 1 can continue receiving vaccinations). This pause will review blinded safety data from these 24 participants, covering the period from the first boost through Day 7 after that boost. At both scheduled pauses, the PSRT will consult the SMC regarding the pause if either of the following conditions are met: 1) one (or more) participants experience an SAE that is related to a study agent, or 2) two (or more) participants experience grade 3 or 4 AEs of the same type (e.g. elevated ALT) related to a study agent. Boost vaccinations for Groups 2-7 will resume once safety data from the booster sentinel cohort have been reviewed by the PSRT and they have concluded it is safe to proceed.

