8 SAFETY AND REPORTING

8.1 ASSESSING AND RECORDING SAFETY PARAMETERS

8.1.1 REACTOGENICITY

8.1.1.1 Diary Card (7-Day Solicited Reactogenicity)

Reactogenicity events are AEs that are common and known to occur following administration of this type of study vaccine. A diary card will be used to aid in the collection of potential reactions.

Temperature and solicited local and systemic symptoms will be recorded in the clinic before vaccination and 30-60 minutes post-injection, at home about 6 hours after vaccination, and then daily by the participant for 7 days. Solicited symptoms that persist after the end of day 7 will be considered an AE or SAE, will be documented, and followed through resolution.

At each vaccination visit, participants will be given a new diary card, a thermometer and a ruler. The diary card will be used as a memory aid, on which the participant will record oral temperature, local and systemic symptoms, and concomitant medications daily for 7 days, beginning with the day of vaccination. Participants will be trained to complete the diary card, how to use the thermometer, and how to measure injection site swelling and redness using the ruler after each vaccination. Completion of the diary card training will be noted in source documents. The diary card is not a source document; the information gained from the review of the diary card and the interview with participants will be documented using a combination of progress notes and CRFs maintained in the participants research chart.

The solicited signs and symptoms on the diary card are:

Local

- Pain/tenderness
- Itching
- Warmth
- Redness/erythema measurement of largest dimension
- Swelling/induration measurement of largest dimension

Systemic

- Fever
- Myalgia
- Arthralgia
- Headache
- Fatigue
- Chills
- Rash
- Nausea

- Dizziness

Where multiple assessments are taken on the same day, participants will be requested to record the day's highest measured temperature and measurement of largest dimension for redness and swelling.

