Follow-up on participant well-being will be performed by telephone (preferred method) or clinic visit on the day following vaccination (and up to 48 hrs. later). Diary cards will be reviewed with the clinician on day 7 ± 2 following each vaccination. If upon reviewing the diary card, the clinician finds that local or systemic information (except swelling, redness, temperature measurements) is missing from the diary card, or the diary card is lost, the participant will be asked to provide the missing information to the best of their recollection. The missing data, such as temperature measurements will be indicated as missing in the database and a lost diary card will not result in a protocol deviation.

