APPENDIX G. PARTICIPANT VISIT SCHEDULE

RV460/WRAIR #2672**Appendix G**
Participant Visit Schedule

Visit No.	Visit Day	Clinic visit activities	Optional Procedures	Approx. Time	Reimbursement
Screening	-45 to -3 days	Screening: Briefing & contact information, informed consents, test of understanding, medical history, vital signs, complete physical exam, 1 TBSP blood draw for: HIV test, hepatitis B and C, syphilis, general health, urine pregnancy test for women, urine test (dipstick) for blood and protein	-Pap smear for women who agree to vaginal secretion collection	4-5 Hours	1000 Ksh
1	0	Vaccination 1*: Enrollment & randomize, exam & eligibility review, vaccination or placebo, examine injection site 30-60 minutes post-injection, receive diary card, urine pregnancy test for women, 12 TBSP blood draw for: research tests & HIV	-Mucosal secretion collection	5 - 6 Hours	1000 Ksh (+1000 Ksh for each mucosal secretion collection)
Phone call or Clinic Visit 24-48 hours After Vaccination					1000 Ksh
2	3	Follow Up: exam & symptom review, review diary card, 2 TBSP blood draw for: research tests. Bring diary card.		2 Hours	1000 Ksh
3	7	Follow Up: exam & symptom review, review & collect diary card, 2 TBSP blood draw for: research tests. Bring diary card.		3 Hours	1000 Ksh
4	14	Follow Up: exam & symptom review, 5 TBSP blood draw for: general health & research tests		2 Hours	1000 Ksh
5	28	Vaccination 2*: Exam & eligibility review, vaccination or placebo, examine injection site 30-60 minutes post-injection, receive diary card, urine pregnancy test for women, 2 TBSP blood draw for: research tests		4 Hours	1000 Ksh
Phone call or Clinic Visit 24-48 hours After Vaccination					1000 Ksh

Visit No.	Visit Day	Clinic visit activities	Optional Procedures	Approx. Time	Reimbursement
6	35	Follow Up: exam & symptom review, Review diary card, 2 TBSP blood draw for: research tests. Bring diary card.		2 Hours	1000 Ksh
7	42	Follow Up: exam & symptom review, 4 TBSP blood draw for: research tests and general health. Urine pregnancy test for women that elect for optional procedure(s). Bring diary card.	-Mucosal Secretion collection	4 - 5 hours	1000 Ksh (+1000 Ksh for each mucosal secretion collection)
8	84	Vaccination 3*: Exam & eligibility review, vaccination or placebo, examine injection site 30-60 minutes post-injection, receive diary card, urine pregnancy test for women, 3 TBSP blood draw for: research tests		4 Hours	1000 Ksh

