Phone call or Clinic Visit 24-48 hours After Vaccination					1000 Ksh
9	87	Follow Up: exam & symptom review, review diary card, 2 TBSP blood draw for: research tests. Bring diary card.		2 Hours	1000 Ksh
10	91	Follow Up: exam & symptom review, review & collect diary card, 4 TBSP blood draw for: research tests. Bring diary card.		3 Hours	1000 Ksh
11	98	Follow Up: exam & symptom review, 9 TBSP blood draw for: general health, HIV & research tests. Urine pregnancy test for women that elect for optional procedure(s).	-Mucosal secretion collection -Lymph node biopsy	5 - 6 Hours	1000 Ksh (+1000 Ksh for each mucosal secretion collection & 5000 Ksh for lymph node biopsy)
Return in 1 week if lymph node biopsy was performed					
12	140	Vaccination 4*: Exam & eligibility review, vaccination or placebo, examine injection site 30-60 minutes post-injection, receive diary card, urine pregnancy test for women, 3 TBSP blood draw for: research tests		4 Hours	1000 Ksh
Phone call or Clinic Visit 24-48 hours After Vaccination					1000 Ksh
13	143	Follow Up: exam & symptom review, review diary card, 2		2 Hours	1000 Ksh

Visit No.	Visit Day	Clinic visit activities	Optional Procedures	Approx. Time	Reimbursement
		TBSP blood draw for: research tests. Bring diary card.			
14	147	Follow Up: exam & symptom review, review & collect diary card, 3 TBSP blood draw for: research tests. Bring diary card.		3 Hours	1000 Ksh
15	154	Follow Up: exam & symptom review, 9 TBSP blood draw for: general health, HIV & research tests. Urine pregnancy test for women that elect for optional procedure(s).	-Mucosal secretion collection	4 - 5 hours	1000 Ksh (+1000 Ksh for each mucosal secretion collection)
16	224	Vaccination 5*: Exam & eligibility review, vaccination or placebo, examine injection site 30-60 minutes post-injection, receive diary card, urine pregnancy test for women, blood draw for: 2 TBSP research tests		4 hours	1000 Ksh
Phone call or Clinic Visit 24-48 hours After Vaccination					1000 Ksh
17	231	Follow Up: exam & symptom review, review diary card, 3 TBSP blood draw for: research tests. Bring diary card.		2 Hours	1000 Ksh
18	238	Follow Up: exam & symptom review, 9 TBSP blood draw for: research tests, general health & HIV. Bring diary card. Urine pregnancy test for women that elect for optional procedure(s).	-Mucosal secretion collection	4 - 5 Hours	1000 Ksh (+1000 Ksh for each mucosal secretion collection)

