APPENDIX I. DIARY CARD

LABEL

Diary Card

Participant ID: | 4 | 6 | 0 | - | | | | | |

Vacc. #: _____

Vaccination Date: _____

DD

MM

YYYY

Short title: Comparative Adjuvant Study for HIV-1 Env DNA and Protein Vaccines in Kenya
 RV460 / WRAIR #2672

13-07-2020
 Version 1.7

Instruction for recording No. 2-7 and 8-15

Please use the grading scale below to record the severity of your reaction to the injections in the next sections:

0 = None**1 = Mild:** minimal interference with usual social and functional activities.**2 = Moderate:** symptoms causing greater than minimal interference with usual social and functional activities.**3 = Severe:** symptoms causing inability to perform usual social and functional activities

Time After vaccination	30-60 min	6 hr	Day 1	Day 2	Day 3	Day 4	Day 5	Day 6	Day 7
Day/Month	__ / __	__ / __	__ / __	__ / __	__ / __	__ / __	__ / __	__ / __	__ / __
Time taken (hrs/min)									
1. Oral temperature (Celsius)									

Vaccination injection site reactions		 Right arm		 Left arm	
2. Injection site pain or tenderness					
3. Swelling (at injection site)					
4. Itching (at injection site)					
5. Redness (measure the largest dimension in cm.)					
6. Hardness (measure the largest dimension in cm.)					
7. Warmth (at injection site)					

General Reactions (not injection site)								
8. Headache								
9. Chills								
10. Dizziness								
11. Tiredness / Fatigue								
12. Nausea								
13. Muscle pain								
14. Joint pain								
15. Rash (if present, describe in "other symptoms")								
16. Took medication for fever or for above symptoms?	0=No 1=Yes							

Other symptoms (please describe):								

LABEL

Diary Card

Participant ID: | 4 | 6 | 0 | - | | | | |

Vacc. #: _____

Vaccination Date: _____

DD

MM

YYYY

Short title: Comparative Adjuvant Study for HIV-1 Env DNA and Protein Vaccines in Kenya
 RV460 / WRAIR #2672

13-07-2020
 Version 1.7

If you take any medication, please record in the table below
 If you take medications for fevers, please check your temperature again after 4 hours and record above in "Other symptoms"

Medication	Dose/route	Reason	Start date	Stop date

Suggestion

- Complete the diary card in as much detail as you can every day, at the same time each day
- Record any problems that occur during this period
- Bring back this diary card with you at the next appointment
- If you forget to record any data, leave it blank

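### The day 7 ± 2 diary visit lets the card be collected before its Day 7 entry, including for both sentinel reviews, and 12 months of MAAE follow-up is met at nominal dates but not guaranteed

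*Protocol*

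**What the plan says.** **Diary.** Section 8.1.1.1 of the protocol sets the review: "Diary cards will be reviewed with the clinician on day 7 ± 2 following each vaccination". The participant visit schedule (Appendix G) adds collection at Visit 3, after dose 1 ("review & collect diary card, 2 TBSP blood draw for: research tests"), and at Visit 14, after dose 4, the first boost ("review & collect diary card, 3 TBSP blood draw for: research tests"). It does the same at Visits 10 and 21, after doses 3 and 6. After doses 2 and 5 (Visits 6 and 17) the card is only reviewed, and the participant is asked to bring it again to the 14-day visit.

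Section 8.1.1.1 has the card filled in "daily for 7 days, beginning with the day of vaccination". The printed card (Appendix I) instead has columns for 30-60 minutes and 6 hours, followed by Day 1 to Day 7. It tells the participant: "If you forget to record any data, leave it blank". Section 8.1.1.1 also states: "Solicited symptoms that persist after the end of day 7 will be considered an AE or SAE".

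Section 5.3 defines the first sentinel review on "blinded safety data from these 24 participants covering the period immediately after their first vaccination through Day 7" and the second on data "covering the period from the first boost through Day 7 after that boost".

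**MAAEs.** Appendix A, footnote 9, follows MAAEs to the end of the study and describes this as 12 full months after the last vaccination. Section 8.1.6 gives the reason, a theoretical autoimmune risk with adjuvants such as ALF43 and dmLT. It defines MAAEs to include hospital, emergency-room, urgent-care and other medical visits. The Protocol Summary and the Precis say that the three weekly calls after week 105 ask about MAAEs. The list in Section 5.5 of what those calls collect includes hospitalizations but not the other kinds of visit.

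**The concern.** Solicited reactogenicity is a primary endpoint, and both sentinel reviews bear on whether Groups 2-7 continue. A card taken away on dose+5 cannot hold later entries. The recall rule in Section 8.1.1.1 lets the clinician ask about missing past information, but it cannot supply days that have not happened. It also excludes temperature, redness and swelling, 3 of the 14 solicited items (5 local, 9 systemic). Nor can such a card show whether a symptom lasted beyond Day 7, the point at which it becomes an AE.

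The 12-month MAAE follow-up is the stated safeguard for the new adjuvants. Its end is a fixed study week, while the last dose has a window of its own and may be given outside that window if the PSRT agrees (Section 5.4; Appendix A, footnote 13).

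**Working it through.** **Diary.** Inputs: review on dose+5 to dose+9 (Section 8.1.1.1) and seven daily entries. If the vaccination day is Day 1, the last entry falls on dose+6. If the next day is Day 1, as the card's columns imply, it falls on dose+7. The counts below assume that the entry for the visit day itself is already made, so they are minimums.

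| Review on | Blank entries, last entry dose+6 | Blank entries, last entry dose+7 |
|---|---|---|
| dose+5 | 1 of 7 | 2 of 7 |
| dose+6 | 0 | 1 of 7 |
| dose+7 to dose+9 | 0 | 0 |

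So one or two of the five permitted review days leave the card incomplete. This counts permitted days and is not an expected frequency. Sentinel cards exposed: 24 participants × 2 doses = 48.

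**MAAE follow-up.** Inputs from Appendix A: dose 6 on day 392 ± 7 and exit visit on day 735 ± 14. Three weekly calls follow, so the last is nominally at week 108 = 108 × 7 = day 756. Follow-up = day of last contact − day of dose 6.

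- The protocol's own figure: 756 − 392 = 364 days = 52 weeks. This reproduces 12 months on the 52-week convention and is one day short of 365.
- End fixed at day 756, dose at +7: 756 − 399 = 357 days. Dose at −7: 756 − 385 = 371 days.
- Calls following an exit visit at −14: last call on day 721 + 21 = 742. With an on-time dose, 742 − 392 = 350 days. With a dose at +7, 742 − 399 = 343 days.
- Dose given k days after nominal with PSRT agreement, end fixed at day 756: 364 − k days. No outer limit on k is stated.

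To reach 365 days after the latest in-window dose, the last contact must fall on day 399 + 365 = 764. That is 764 − 756 = 8 days after week 108, or 764 − 742 = 22 days after the last call if calls follow the earliest exit visit.

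**The case against.** **On the diary.**
- The card is a memory aid and not a source document, so the data come from review and interview (Sections 8.1.1.1 and 11.1). This stands, but an interview on dose+5 cannot reach Day 7 either.
- Every dose has a 14-day visit with a symptom review, and a symptom that persists becomes an AE followed to resolution. This also stands and covers persistence in part. That visit falls on dose+11 to dose+17, however, after the Day 7 cut-off of the sentinel reviews.
- The sentinel reviews must cover data through Day 7 whatever the visit window allows. True, but no step is given for obtaining the remaining entries once the card is collected.
- Section 8.1.1.1 also describes a 6-hour reading followed by seven daily ones, which agrees with the card. The Day 1 conflict is therefore with one sentence of that section, which still needs reconciling.

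A reader might infer that peak severity is lost or that regimens are biased against each other. The documents do not support that. Section 7.2.2 reports maximum severity, Section 2.2.3.2 says local reactions to gp120 protein vaccines generally resolved within 3 days, and the same windows apply to all seven groups.

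**On MAAEs.**
- A reader might infer that 12 months is not delivered at all. At nominal dates it is, on the 52-week convention.
- A reader might also infer from the Section 5.5 list that follow-up of non-hospital MAAEs stops at the exit visit: 735 − 392 = 343 days nominally, and from 721 − 399 = 322 to 749 − 385 = 364 within the windows. The Protocol Summary, the Precis and footnote 9 say otherwise, so this is a mismatch to reconcile and not evidence that follow-up stops.
- Potentially immune-mediated conditions are separately recorded to the end of the trial (Section 7.2.2) and reported in an expedited manner (Section 8.2.1.1). This limits the consequence of a short MAAE follow-up.

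**On visit timing.** Reading Appendix A as leaving post-dose visits untied to the actual dose goes too far. Footnotes 6 and 10 and Section 8.1.1.1 time the 24-hour contact and the diary review from the vaccination. At most, a footnote could state the anchor for the 3-day and 14-day visits.

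**Conclusion.** The diary point holds. The permitted window and the instruction to collect, taken together, allow the card to be closed one or two days early after four of six doses, including both sentinel doses. The loss is confined to late or persisting reactions on the last one or two days. It matters most for the two sentinel reviews, and how often it would happen cannot be derived from the protocol.

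The MAAE point holds only as not guaranteed. Nominal follow-up is 364 days. It falls to 357 for a late in-window dose and to 343 only when that dose is combined with calls following an exit visit at −14. It is shorter still for sufficiently late out-of-window doses. These figures assume that calls end either at a fixed week 108 or 21 days after the actual exit visit, since the protocol does not say which. The Section 5.5 call list also does not match the purpose stated elsewhere for the calls.

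Both points should be corrected. Neither undermines the design.

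**What to change.** 1. Reconcile Section 8.1.1.1 with the printed card on what Day 1 is.
2. Keep the ± 2 visit window, but collect or close out the card only after Day 7 is complete: dose+7 to dose+9 if the vaccination day is Day 1, dose+8 to dose+9 if the next day is. Both lie inside the present upper limit. If the visit is earlier, the participant keeps the card and the remaining entries are reviewed by phone or brief visit by dose+9. For the 24 sentinel participants, do this before the data go to the PSRT.
3. Time the last MAAE contact no earlier than 12 months after the participant's actual last vaccination.
4. Add MAAEs, as Section 8.1.6 defines them, to the Section 5.5 call list.

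The cost is wording, one added call question, and a short contact when the 7-day visit is early. The sentinel reviews wait at most until dose+9. For an in-window last dose the final call moves by at most 8 days (22 if calls follow the actual exit visit), to day 764 at the latest, and the stated 108 weeks must be adjusted. If the 26 months of availability in inclusion criterion 1 run from enrollment (26 × 365/12, about 791 days), they already cover this. No vaccination window changes.

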8.1.2 MANAGEMENT OF VACCINATION REACTIONS

Participants will be observed in the KEMRI/USAMRD-A CRC by study staff for 30 to 60 minutes after vaccination. On vaccination days, there will be at a minimum one physician investigator available for assessment of any reaction.

In the event of a severe allergic reaction, the CRC is staffed with trained medical personnel and stocked with appropriate medical emergency equipment to provide acute care for conditions such as anaphylaxis. If needed, participants will be transferred to the Unilever Hospital for further assessment and care.

8.1.3 ADVERSE EVENTS (AES)

ICH E6 defines an AE as any untoward medical occurrence in a patient or clinical investigation participant administered a pharmaceutical product regardless of its causal relationship to the study treatment. FDA defines an AE as any untoward medical occurrence associated with the use of a drug in humans, whether considered drug related.

An AE can therefore be any unfavorable and unintended sign (including an abnormal laboratory finding), symptom, or disease temporally associated with the use of medicinal (investigational) product. The occurrence of an AE may come to the attention of study personnel during study visits and interviews of a study recipient presenting for medical care, or upon review by a study monitor.

All AEs, including solicited local and systemic reactions, will be documented and included as source for the eCRF and maintained in the participant's research chart. Information to be collected for AEs includes:

- Event description
- Date of onset
- Assessment of severity
- Relationship to study product and

- Alternate etiology (assessed only by those with the training and authority to make a diagnosis and listed on the form FDA 1572 as an investigator)
- Date of resolution
- Seriousness and
- Outcome

AEs occurring during the trial collection and reporting period will be documented appropriately regardless of relationship. AEs will be followed through resolution. Any medical condition that is present at the time that the participant is screened will be considered as baseline and not reported as an AE. However, if the severity of any pre-existing medical condition increases, it should be recorded as an AE.

An SAE: An adverse event or suspected adverse reaction is considered "serious" if, in the view of either the investigator or sponsor, it results in any of the following outcomes: death, a life-threatening adverse event, inpatient hospitalization or prolongation of existing hospitalization, a persistent or significant incapacity or substantial disruption of the ability to conduct normal life functions, or a congenital anomaly/birth defect. Important medical events that may not result in death, be life-threatening or require hospitalization may be considered serious when, based upon appropriate medical judgment, they may jeopardize the participant and may require medical or surgical intervention to prevent one of the outcomes listed in this definition. Examples of such medical events include allergic bronchospasm requiring intensive treatment in an emergency room or at home, blood dyscrasias or convulsions that do not result in inpatient hospitalization, or the development of drug dependency or drug abuse (21 CFR 312.32).

"Life-threatening" refers to an adverse event that at occurrence represents an immediate risk of death to the participant. An event that may cause death if it occurs in a more severe form is not considered life-threatening. Similarly, hospital admission for an elective procedure is not considered an SAE. The clinician will ask each participant about other interim adverse experiences and record this information in the source documents. Study staff will enter AE or SAE information into the study database within three business days of the participant visit. After study day 28 after the last vaccination, only SAEs and new chronic medical conditions that require ongoing medical management will be entered into the database, through the last study visit. All other adverse events will be recorded on source documents only. The PI or designee will assess the relationship of the study product to the events.

If an event meets both the criteria of a study endpoint and an adverse event, the event will be reported either as a study endpoint or as an adverse event (not both).

